7.22.5.2 Eliciting Adverse Events

Patients should be asked non-leading questions (eg, “How do you feel?”) and further questions should be posed if there is indication of an AE. The questioning should be conducted with due regard for objectivity and, in particular, the questioner should gather information regarding AEs from questioning the patient, the patient’s parent/guardian, spontaneous report by the patient or parent/guardian, laboratory reports, and any health care provider’s observations.

The onset date, resolution date, treatment administered, and outcome of each AE must be recorded on the appropriate eCRF. The relationship of each AE to study medication must be recorded. In addition AEs may be considered to be related to the IDDD, the IDDD surgical procedure, or the IT administration process. Since the AE may be deemed to be related to more than one of these factors, as many of these IDDD-related options as apply should be indicated on the eCRF.

7.22.5.3 Protocol Deviations for Medical Emergency or Adverse Event

During and following a patient’s participation in the study, the Investigator should ensure that adequate medical care is provided to a patient for any AEs, including clinically significant laboratory test results.

The Investigator should inform the patient, the patient’s parent(s), or the patient’s legally authorized representative when medical care is needed for intercurrent illness(es) of which the Investigator becomes aware. In an emergency situation, the Investigator should contact the Shire Medical Monitor (see Section [7.22.5.1](#)).

Only when an emergency occurs that requires an immediate deviation from the protocol for the safety of a patient, will there be such a deviation and this will be only for that patient.

The Investigator or other physician in attendance in such an emergency must contact the Shire Medical Monitor as soon as possible.

The Investigator, along with the Shire Medical Monitor, will make a decision as to whether or not the patient should continue in the study prior to the next scheduled dose. The departure from the protocol and the grounds for it should be stated in the eCRF.

7.23 Abuse, Overdose and Medication Errors

Abuse, misuse, overdose or medication error must be reported to the Sponsor according to the SAE reporting procedure whether or not they result in an AE/SAE as described in Section 7.22.

- **Abuse** – Persistent or sporadic intentional intake of investigational medicinal product at a dose higher than prescribed per protocol (but below the dose defined for overdose) or when used for non-medical purpose (eg, altering one’s state of consciousness)
- **Misuse** – Intentional or unintentional use of investigational medicinal product other than as directed or indicated at any dose, which is at or below the dose defined for overdose (Note: This includes a situation where the test article is not used as directed at the dose prescribed **by the protocol**)
- **Overdose** – Overdosage with adverse clinical consequences is not anticipated with the use of HGT-1410. Additionally, HGT-1410 will be given in a clinical setting by a health care provider.
- **Medication Error** – A mistake made in prescribing, dispensing, administration and/or use of the investigational medicinal product.

7.24 Safety-related Study Stopping Rules

If any patient experiences a life-threatening (Grade 4) adverse event or death which is considered by the sponsor to be possibly, probably, or definitely related to study drug **or the IDDD**, or if 2 or more patients experience a Grade 3 adverse event during the trial that is considered by the sponsor to be possibly, probably, or definitely related to the study drug **or the IDDD**, then the site will be instructed to halt further HGT-1410 administration to all patients and the safety data reviewed. Following a review of safety data, the study will be either:

- Resumed unchanged
- Resumed with modifications to the protocol or
- Terminated

Patient safety will be monitored on a continuous basis during this study until the last patient completes his or her last scheduled study visit/assessment.

7.25 Pregnancy

Pregnancy and breast feeding are exclusion criteria. Only female patients who have reached menarche will be tested for pregnancy in HGT-SAN-067. If applicable, this will occur at study start and before each dose of HGT-1410 throughout the study. Pregnancy testing will be performed on a blood or urine sample. Patients with a positive or inconclusive result will not be eligible for this study.

At study start, a pregnancy test will be performed if more than 30 days have passed since the initial screening sample. Throughout the study pregnancy testing will occur prior to each dose of HGT-1410. The clinical site’s local laboratory will analyze and report all pregnancy testing results. If a pregnancy test is positive the patient will be discontinued from the study, and the Investigator must contact the Shire Medical Monitor.

Pregnancy is not to be reported as an AE; the Pregnancy Reporting Form, found in the Study Operations Manual along with instructions for completion, should be used to report the pregnancy. The pregnancy will be followed up through delivery or final outcome.

7.26 Removal of Patients from the Trial or Study Drug

The patient's parent or legally authorized representative acting on behalf of the patient is free to withdraw consent and discontinue participation in the study at any time without prejudice to further treatment. Since this is an extension trial, there will be no replacement of patients who discontinue the study for any reason.

A patient's participation in the study may be discontinued at any time at the discretion of the Investigator, Sponsor, or Medical Monitor. The following may be justifiable reasons for the Investigator, Sponsor, or Medical Monitor to remove a patient from the study:

- Adverse Event: If a patient experiences an AE which, in the judgment of the investigator, the sponsor, or the medical monitor, presents an unacceptable consequence or risk to the patient.
- Adverse Laboratory Experience: If a patient has an adverse laboratory experience which, in the judgment of the investigator, the Sponsor, or the medical monitor, presents an unacceptable consequence or risk to the patient, the patient may be withdrawn from the study.
- Comorbidity: If a patient develops comorbidity during the course of the study that is independent of the study indication, and treatment is required that is not consistent with protocol requirements.
- Intercurrent Illness: If a patient develops an illness during the course of the study that is not associated with the condition under study, and which requires treatment that is not consistent with protocol requirements.
- Refusal of Treatment: If the patient, the patient's parent(s) or legally authorized representative(s) discontinues participation in the study, or the patient is discontinued by the Investigator, reasonable efforts will be made to follow the patient through the end of study assessments. The reason for refusal will be documented on the eCRF.
- Withdrawal of Informed Consent: A patient's parent or legally authorized representative may withdraw his informed consent to participate in the study at any time.
- Cerebrospinal fluid leukocyte count >100 cells per cubic millimeter for 2 consecutive months.
- New onset seizure.
- Anaphylactic reaction beyond reasonable management as described in the Investigator's Brochure.
- Clinically problematic intubations or extubations, which may preclude safe airway management and anesthesia.
- Development of refractory spinal fluid leakage.
- Clinically significant prolonged (eg, greater than 24 to 48 hours) worsening in mental status, including development of new focal or non-focal neurological symptoms, or recurrence of a previously stable prior medical problem judged due to study drug or participation that is exclusive of effects from anesthesia.
- Non-compliance, including failure to appear at 1 or more study visits.

- The patient was erroneously included in the study.
- The patient develops an exclusion criterion.
- The study is terminated by the Sponsor.
- The patient becomes pregnant during the trial.

If a patient discontinues the study the Patient Completion/Discontinuation eCRF describing the reason for discontinuation must be completed. Any AE's experienced up to the point of discontinuation must be documented on the AE eCRF.

If AEs are present when the patient withdraws from the study, the patient will be re-evaluated within 30 days of withdrawal. All ongoing SAEs at the time of withdrawal will be followed until resolution.

At the time of discontinuation or withdrawal, patients will be asked to participate in all safety and efficacy evaluations required for the end of study visit and for the safety follow-up visit. Participation in these EOS procedures will be strongly encouraged, but is voluntary for those patients electing to discontinue from the study. The patient will be scheduled for the removal of the IDDD.

7.27 Other Study Procedures

This section is not applicable.

7.28 Appropriateness of Measurements

The neurocognitive and developmental assessments are intended to gauge which domains can be accurately measured, with which specific tools, despite the considerable behavioral and cognitive challenges in Sanfilippo syndrome. The evaluation of these domains and the analysis of CSF, serum, and urine biomarkers may provide the pivotal data necessary to inform the clinical assessments and biomarkers used in possible future Sanfilippo syndrome ERT trials.

8 STUDY ACTIVITIES

Patients who participated in Study HGT-SAN-055 through Week 26 and completed the EOS evaluations may be eligible for enrollment in this open-label extension study. Informed consent (and assent, if applicable) must be obtained prior to performing any study related procedures that are specific to HGT-SAN-067. Informed consent may be obtained anytime from Week 20 in HGT-SAN-055. This would allow a patient to have a nonfunctional IDDD replaced or revised prior to the first HGT-1410 dose in HGT-SAN-067.

8.1 Screening Visit/Study Start Visit

All Screening assessments for this study are to have been performed during the Week 26 EOS procedures in HGT-SAN-055 (ie, 30 [\pm 7] days after the last HGT-1410 administration). If less than 60 days have elapsed since completion of the EOS assessments for HGT-SAN-055, and the start of HGT-SAN-067, the assessments detailed in this Screening visit do not need to be repeated. The Baseline visit for this study will be the first day the patient received their first dose of HGT-1410 in the HGT-SAN-055 Study.

If more than 60 days have elapsed following the HGT-SAN-055 EOS procedures, patients will be evaluated for enrollment in HGT-SAN-067 on a case-by-case basis by the Investigator. A decision about enrollment will be made following discussion with the Medical Monitor. If the patient is enrolled, the following assessments are to be repeated within 30 days prior to the first scheduled intrathecal HGT-1410 dose:

- Physical examination
- Height and weight
- Head circumference
- ECG
- Vital signs
- Hematology
- Leukocyte pellet preparation to be used for additional disease-related laboratory studies, including possible assessment of cross-reactive immunologic material (if this is not collected at baseline, it can be collected at any subsequent pre-dosing time point)
- Serum chemistry
- Pregnancy testing (for post menarche premenopausal females only)
- Urinalysis
- Urine GAG, including heparan sulfate and heparan sulfate derivatives
- Plasma collection for biomarkers
- Anti-rhHNS antibody testing (serum and CSF)
- General anesthesia: administration of anesthesia will be given prior to the following assessments:
 - ABR
 - MRI of the head
 - Neurological examination (performed prior to the administration of anesthesia)

- Full Neurodevelopmental assessments, including Vineland Adaptive Behavior Scales, Second Edition (VABS-II; all assessments performed prior to the administration of anesthesia)
- CSF sample collection (chemistry, cell count, heparan sulfate and heparan sulfate derivatives, and other MPS exploratory biomarkers) via the IDDD
- Children's Sleep Habits Rating Scale
- CHQ-50
- CHQ-87
- ITQOL
- Concomitant medications, therapies, and procedures
- AE assessments

8.2 Treatment: Drug Administration and Weekly Assessments

Patients will receive HGT-1410 IDDD monthly (Q4W), on Day 2 (± 2 days), Week 1.

Patient assessments for safety, biochemical, and neurological baseline measures (Day 1, Week 1) will occur on the day before the first IT injection. Note: Day 1 assessments may be performed on the same day as the administration of study drug (Day 2). This can occur if it is feasible for the patient to arrive at the study site early in the day, and if it is deemed clinically appropriate by the Investigator. If the procedures on Day 1 and Day 2 are combined in this way, the assessments will be recorded as occurring on Day 2.

CSF samples will be obtained from these patients on Day 2, immediately prior to the first IT study drug injection.

8.2.1 Week 1

8.2.1.1 Day 1 (Pre-treatment) Assessments Performed Prior to Each Dose

- Physical examination
- Height and weight
- Vital signs
- Hematology (after Month 54 frequency reduced to Q3 Months)
- Serum chemistry (after Month 54 frequency reduced to Q3 Months)
- Urinalysis (after Month 54 frequency reduced to Q3 Months)
- Pregnancy testing (applicable females only)
- Neurological examination (performed prior to the administration of anesthesia and the HGT-1410 IT injection)
- Concomitant medications, therapies, and procedures
- AE assessments

Note: If the HGT-SAN-055 EOS (or HGT-SAN-067 Screening) assessments were performed within 7 days of first intrathecal HGT-1410 treatment in this study, the pre-treatment assessments described in this section do not need to be completed prior to the first treatment in study HGT-SAN-067.

DAY 1 (PRE-TREATMENT) ADDITIONAL ASSESSMENTS PERFORMED AT MONTHS 12, 24, 36, 54, 66, AND 78

- Head circumference
- Visual and hearing assessments
- Urine GAG, including heparan sulfate and heparan sulfate derivatives (also performed at Month 60 and Month 72, ie, Q6 Months following Month 54)
- Plasma collection for biomarkers
- Anti-rhHNS antibody testing (also performed at Month 60 and Month 72, ie, Q6 Months following Month 54)
- ABR (not performed after Month 54, ie not on Month 66 or 78)
- MRI of the head
- Full neurodevelopmental testing, including VABS-II (performed prior to the administration of anesthesia and the HGT-1410 IT injection)
- Children's Sleep Habits Rating Scale
- Child health questionnaire-50
- Child health questionnaire-87
- Infant toddler QoL Questionnaire

8.2.1.2 Day 2 (± 2 days) Assessments and Administration of HGT-1410

Patients may be discharged from the clinical site 4 hours after dosing, if deemed stable by the Investigator.

- Physical examination (after Month 54 the full physical examination will be performed at Months 54, 66, and 78. The remainder of the physical examinations will be symptom-directed)
- ECG (performed following IT study drug injection)(after Month 54 performed Q3 months)
- Vital signs
- CSF sample collection (obtained prior to IT study drug injection)
- HGT-1410 IT injection (Day 2 ± 2 days)
- Neurological examination
- Concomitant medications, therapies, and procedures
- AE assessments

The neurological exam should not occur sooner than 4 hours after study drug administration or before the patient has fully recovered from any anesthesia administered for the dosing, whichever occurs later.

8.3 End of Study/Early Termination Procedures: Month 79

Patients who complete the study or who discontinue prior to the end of the study, will have EOS assessments performed 30 (± 7 days) after their last dose of HGT-1410.

Patients who discontinue or are withdrawn prior to study completion will be asked to participate in the EOS procedures at the time of discontinuation. Participation in these EOS procedures will be strongly encouraged, but is voluntary for those patients electing to discontinue from the study. Note: Patients will have the IDDD removed when they discontinue from the study, unless the patient is continuing to receive treatment through another mechanism (eg, expanded access, commercially available).

- Physical examination
- Height and weight
- Head circumference
- Visual and hearing assessment
- ECG
- Vital signs
- Hematology
- Serum chemistries
- Urinalysis
- Urine GAG, including heparan sulfate and heparan sulfate derivatives
- Anti-rhHNS antibody testing (serum and CSF)
- MRI of the head (unless performed at Month 78)
- CSF sample collection (unless performed at Month 78)
- Neurological examination
- Full neurodevelopmental testing, including VABS-II
- Children's Sleep Habits Rating Scale
- CHQ-50
- CHQ-87
- Infant toddler QoL Questionnaire
- Concomitant medications, therapies, and procedures
- AE assessments

All patients who discontinue the study early will have their IDDD removed.

Patients who withdraw or discontinue after having received fewer than 3 IT injections will not need to complete the EOS visit.

Patients who withdraw or discontinue from the study after having received 3 or more IT injections, will be asked to complete the EOS visit and undergo all the scheduled assessments.

8.4 Safety Follow-up (by Telephone or Visit) Month 80

Patients who complete the study or withdraw early will have a safety follow-up telephone call or visit 30 Days (± 7 days) after the last study visit. This will assess:

- Concomitant medications, therapies, and procedures
- AE assessments

9 QUALITY CONTROL AND ASSURANCE

Training will occur at an investigator meeting or at the site initiation visit or both, and instruction manuals (eg, laboratory manuals and pharmacy manuals) will be provided to aid consistency in data collection and reporting across sites.

Clinical sites will be monitored by Shire or its designee to ensure the accuracy of data against source documents. The required data will be captured in a validated clinical data management system that is compliant with the Food and Drug Administration (FDA) 21 Code of Federal Regulations (CFR) Part 11 Guidance. The clinical trial database will include an audit trail to document any evidence of data processing or activity on each data field by each user. Users will be trained and given restricted access, based on their role in the study, through a password protected environment.

Data entered in the system will be reviewed manually for validity and completeness against the source documents by a clinical monitor from Shire or its designee. If necessary, the study site will be contacted for corrections or clarifications; all missing data will be accounted for.

SAE information captured in the clinical trial database will be reconciled with the information captured in the Pharmacovigilance database.

10 PLANNED STATISTICAL METHODS

10.1 General Statistical Methodology

This is an open-label extension of study HGT-SAN-055 to evaluate the long-term safety and clinical outcomes of intrathecal administration of HGT-1410 in patients with MPS IIIA. The statistical methodology supporting the trial will focus on descriptive rather than inferential approaches, given the early phase and objectives of this trial.

Data will be summarized by dose group (10 mg, 45 mg, and 90 mg) with respect to demographic and baseline characteristics, efficacy variables, and safety variables. Summary statistics for continuous variables will include the n, mean, standard deviation, median, minimum and maximum. Categorical variables will be summarized in a contingency table by the frequency and percentage of patients in each category. Data will be plotted to assess trends across time as appropriate.

No a priori hypotheses will be tested. Exploratory hypotheses may emerge from the data analysis, in which case, appropriate testing methods will be applied and specified in the statistical analysis plan.

There are no formal hypotheses associated with the evaluation of the safety and performance of the IDDD device (SOPH-A-PORT Mini S). All analyses of device safety and performance will be descriptive and no statistical testing will be performed. Device related analyses will be based on patients for whom the device implant procedure was performed and are described in the sections below.

10.2 Determination of Sample Size

Since this is an extension study, sample size is determined by the number of patients who completed HGT-SAN-055 (maximum of 12 patients) and elected to continue treatment with HGT-1410 in this study. Hence no statistical estimation of the sample size was performed.

10.3 Analysis Populations

The primary analysis population consists of all eligible patients from HGT-SAN-055 who have agreed to participate in the extension study. This population will be used to perform both safety and efficacy analyses. The collection of detailed data pertaining to the SOPH-A-PORT mini S will permit device-related analyses to be conducted in the subset of patients in the primary analysis population who had the SOPH-A-PORT Mini S implant procedure performed.

10.4 Demographics and Baseline Characteristics

Patient disposition for those enrolled will be presented in a summary table using number and percentage of patients enrolled, completed or discontinued/withdrew. The reasons for discontinuation/withdrawal will also be presented.

Demographic and baseline characteristics (eg, age, race, ethnicity, medical history, and surgical history) will be reported in summary tables.

10.5 Statistical Analysis of Pharmacokinetic Variables

Not applicable.

10.6 Efficacy, Safety, and Pharmacodynamic Evaluations

10.6.1 Primary Analyses

10.6.1.1 Safety Analysis

In general, safety assessments will be based on all assessments post-baseline. The assessment of safety will be based primarily on the frequency of AEs, and on the frequency of clinically notable abnormal vital sign and laboratory values. Changes from baseline will be calculated by subtracting the baseline value from the post-baseline value.

All enrolled patients who had an IDDD surgical procedure and/or received administration of HGT-1410 will be included in the safety analysis.

Adverse events will be recorded throughout the study and at early termination. Adverse events and medical conditions will be coded using the Medical Dictionary for Regulatory Activities (MedDRA).

Adverse events will be summarized by presenting, for each dose group, the number and percentage of patients having any AE, having an AE in system organ class, and having each individual AE. In addition, those events which resulted in death or were otherwise classified as serious will be presented in a separate listing. The incidence of treatment-emergent adverse events, defined as all AEs from the time of the surgery for IDDD implantation to the last follow up contact, ie, 30 days after the last HGT-1410 administration, (new or worsened from baseline) will be summarized by system organ class, severity, type of adverse event and relationship to trial medication/procedure.

Treatment-emergent AEs deemed related to HGT-1410 administration will be summarized separately.

IDDD and procedure-related AEs will be summarized within system organ class by preferred term. IDDD and procedure-related AEs will be tabulated by severity (mild, moderate, severe) and degree of relatedness. Separate tabulations will be provided for adverse events related to the IDDD, device surgical procedure (including post-implant infections) and IT administration process. These summaries will be presented by device and overall, as appropriate.

Descriptive summaries of clinical laboratory evaluations (hematology, serum chemistry, urinalysis and CSF) results will be presented in summary tables by evaluation visit. Changes from baseline will be summarized for each post-baseline visit. Each laboratory result will be categorized as a patient having had (1) an Abnormal and Clinically Significant (CS) value at any time, (2) no CS values at any time but had at least one Abnormal and not CS (NCS) value, and (3) no CS or NCS values at any time; the number and percentage in each category will be presented. For any patient who experiences a CS laboratory result at any time that was not CS at

baseline (or the most recent non-missing value prior to the start of the treatment), their entire profile for that particular laboratory parameter will be presented as a listing.

The observed values and changes from baseline for vital sign data will be summarized for each dose group. Shift tables may be presented, utilizing reference ranges. Patients with notably abnormal values will be identified and listed separately along with their values.

The observed values and changes from baseline for ECG data will be summarized for each dose group. Patients with any clinically significant findings and/or conduction abnormalities will be listed separately along with their values.

Anti-rhHNS antibody formation will be monitored throughout the study. Results will be presented in summary tables by number and percentage of positive and negative specimens by evaluation visit, and number and percentage of positive and negative specimens overall. The effect of antibodies on other safety parameters will be assessed by presenting summary tables by antibody status.

For those patients who fail to complete the study, the reason for discontinuation will be listed by patient and dose group.

Listings of all study safety data will be presented.

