4.3 Study Duration and Dates

The study duration allows patients who completed Study HGT-SAN-055 and elected to continue treatment with HGT-1410 in Study HGT-SAN-067 to receive treatment with HGT-1410 up to 8 years.

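### Section 10.6.1.1 summarises adverse events over 6 years as crude percentages of patients with no patient-time, and its three laboratory categories ignore baseline status

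*Protocol*

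**What the plan says.** The section opens with its priority: "The assessment of safety will be based primarily on the frequency of AEs", together with the frequency of clinically notable abnormal vital signs and laboratory values. It then names the adverse event measure: "Adverse events will be summarized by presenting, for each dose group, the number and percentage of patients having any AE". The full list of what is counted is "the number and percentage of patients having any AE, having an AE in system organ class, and having each individual AE". The incidence of treatment-emergent events "will be summarized by system organ class, severity, type of adverse event and relationship to trial medication/procedure". Drug-related events get a separate summary, and deaths and other serious events a separate listing. No patient-time denominator, rate or time window is stated for any adverse event output.

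For laboratory results, each patient falls into one of three categories. The first is "an Abnormal and Clinically Significant (CS) value at any time". The second is "no CS values at any time but had at least one Abnormal and not CS (NCS) value". The third is neither. The same paragraph adds a listing of the full parameter profile for any patient with a clinically significant value that was not so at baseline, and states: "Changes from baseline will be summarized for each post-baseline visit".

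Other parts of the protocol bear on this:
- Section 4.3 (Amendment 6) sets a duration of 6 years.
- Section 7.22.1.1 has every adverse event recorded whatever its severity or cause, and Section 7.2 makes any change from the screening physical examination an adverse event.
- Section 7.26 does not replace patients who discontinue.
- Section 6.4 moves Group 1 from 10 mg to 45 mg.
- Section 10.6.2.1 plans, for device failures and malfunctions, a rate with a 95% confidence interval and a time to first failure with a censoring rule.

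**The concern.** The percentage of patients with at least one event rises with observation time as well as with risk. In a progressive childhood disease, with every event and every examination change recorded for years, the overall percentage can reach its ceiling in each dose group whatever the drug does. Below the ceiling, two groups with the same underlying rate will show different percentages if one was followed for less time, and with at most 12 children a single early departure is enough to do this. Group 1's whole-period percentage also combines time at two doses.

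The laboratory table has a separate weakness. A child who was abnormal at baseline and stays abnormal enters the same cell as a child who became abnormal on treatment.

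At stake is whether the frequencies on which safety is primarily to be judged can be read across groups and over time.

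**Working it through.** The protocol states no expected event rate, group sizes or hypothesis, so it has no figure to reproduce. The rates below are assumptions, shown as ranges.

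**Overall any-event percentage.** With a constant rate r per patient-year over T years, P(at least one) = 1 − exp(−rT). With T = 6:

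| r | P(any event) |
|---|---|
| 0.25 | 1 − exp(−1.5) = 77.7% |
| 0.5 | 1 − exp(−3) = 95.0% |
| 1 | 1 − exp(−6) = 99.75% |
| 2 | 1 − exp(−12) = 100.0% |

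Doubling the rate from 1 to 2 moves the percentage by 0.25 points. Doubling from 0.5 to 1 moves it by 4.7 points. If a dose group had 4 patients (assumed), all 4 would have an event with probability 0.9975⁴ = 0.99 at r = 1.

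**Single event terms.** At r = 0.02, 0.05 and 0.1, the 6-year percentages are 11.3%, 25.9% and 45.1%. These are not saturated, but they depend on follow-up: at r = 0.1, a patient who leaves after 2 years has 1 − exp(−0.2) = 18.1%, against 45.1% for one who stays 6 years.

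**Laboratory categories.** Section 8.2.1.1 gives haematology, chemistry and urinalysis at each dose to Month 54, then every 3 months. Months 7 to 54 give 48 draws and Months 57 to 78 give 8, so 56 in all. For one parameter with an assumed chance p of a flagged value per draw, P(ever) = 1 − (1 − p)^56 if draws are independent:
- any out-of-range value, p = 5%: 94.3%; p = 2.5%: 75.8%
- clinically significant value, p = 0.05%, 0.1%, 0.5%, 1%: 2.8%, 5.4%, 24.5%, 43.0%

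Repeat values in one child are correlated. For p = 5% with normal values and a common within-child correlation of 0.3, 0.5 or 0.7, the 94.3% falls to about 83%, 65% or 42%. The main laboratory fault is therefore not saturation. It is that none of the three definitions refers to the baseline value; only the listing of new clinically significant values does.

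**What a rate would show.** Assume 4 patients × 6 years = 24 patient-years per group. Then 24 events give 1.00 per patient-year (exact Poisson 95% CI 0.64 to 1.49) and 48 events give 2.00 (1.47 to 2.65). The crude percentages expected at those two rates are 99.75% and 100.0%.

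**The case against.** The strongest reply is that Section 10.6.4 leaves final analyses and presentations to the statistical analysis plan, that patient-year rates and shift tables are ordinary content of such a plan, and that a descriptive study with no hypothesis has no decision resting on the crude percentages. The plan may indeed add these outputs. But Section 10.6.1.1 does not leave the measure open. It names it, and it names the laboratory categories, so the criticism is of a stated method. Section 10.6.2.1 shows that the sponsor was ready to specify a rate and a censored time to event in the protocol for the device.

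The reply is right about scope. A reader might infer that all the primary safety results are percentages heading to 100% in every dose group. The documents do not support that. The section also plans severity, relatedness, drug-related and serious-event outputs, by-visit laboratory changes, vital sign, ECG and antibody summaries, and listings of all safety data. With at most 12 children, listings carry much of the information. Single events and clinically significant laboratory values stay well below the ceiling at the assumed rates.

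A reader might also attach 8 years to this analysis. That figure comes from Amendment 7, Section 4.3 ("treatment with HGT-1410 in Study HGT-SAN-067 to receive treatment with HGT-1410 up to 8" years). The quoted analysis is Amendment 6, and Amendment 7's Section 10 is not shown. At 8 years the any-event figure for r = 1 would be 99.97%, so this conclusion does not turn on the version.

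Finally, rates would add only modest precision: the two intervals above just overlap despite a true doubling. That stands as a limit on what the change can deliver.

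**Conclusion.** The point holds in a limited form. The overall any-event percentage says little after 6 years if the background rate is about 0.5 per patient-year or more; at 0.25 it is 77.7% and still has room to move. Class and single-event percentages remain usable but mix risk with length of follow-up. The three laboratory categories cannot tell a persisting abnormality from a new one. The other summaries in the section are not affected by saturation in this way.

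It would go too far to say that the plan cannot show change over time or cannot distinguish dose groups at all: the by-visit laboratory summaries address time, and the unsaturated percentages are confounded by follow-up rather than void. The sizes rest on assumed constant rates, an assumed 4 patients per group and assumed per-draw probabilities, none of which the protocol gives. This is a change worth making, not a flaw that invalidates the safety analysis.

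**What to change.** In Section 10.6.1.1:

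1. Add event counts and rates per patient-year with 95% confidence intervals for any adverse event, related events, serious events and each system organ class. Define patient-time to match the window in which treatment-emergent events are counted.
2. Show these rates by period on treatment and, for Group 1, by the dose being received when the event occurred.
3. Replace or supplement the three laboratory categories with a shift table of baseline category by worst post-baseline category.
4. Keep the crude numbers and percentages of patients alongside.

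The data are already collected, so the cost is wording and table shells. There are three downsides. A rule is needed for counting recurrent episodes of the same event. An exact Poisson interval ignores between-child variation and will be somewhat too narrow. Without a control group, the rates describe risk over time and exposure but do not by themselves show drug-caused harm.
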